## 3.5 Exploratory variables

### 3.5.1 Supportive efficacy and health related quality of life variables

The supportive efficacy and health related quality of life endpoints are summarised in section 1.1.4.

#### 3.5.1.1 Daily Sleep Interference Scale (DSIS)

DSIS is an 11-point Likert scale used to assess how pain interferes with participants' sleep where 0= pain did not interfere with sleep and 10 = pain completely interfered with sleep. This will be recorded on a daily basis (upon awakening) via electronic patient recorded

outcome (ePRO) diary until Week 18 unless participants discontinue the IP early in which case last recording DSIS would be at ET visit.

The derivation of the averages will be the same as for the NRS pain score described in section 3.2 including the handling of the ET assessments. However, the average will be derived regardless of how many daily scores are available.

### **3.5.1.2 European Quality of Life-5 Dimensions (EQ-5D-5L)**

The EQ-5D-5L questionnaire assesses 5 dimensions of health (mobility, self-care, usual activities, pain/discomfort, and anxiety/depression). For each dimension, respondents will select which statement best describes their health on that day from a possible 5 options of increasing levels of severity (no problems, slight problems, moderate problems, severe problems, and extreme problems).

In addition to the descriptive system, the participants are asked to rate their health on the day of assessment on a visual analogue scale (VAS), ranging from 0 (worst imaginable health) to 100 (best imaginable health). This score is reported separately.

The European Quality of Life-5 Dimensions (EQ-5D-5L) may be analysed separately and not form part of this SAP.

### **3.5.1.3 36-Item Short Form Health Survey Questionnaire**

The 36-Item Short Form Health Survey Questionnaire version 2 (SF-36v2) is a 36-item questionnaire on functional health and well-being, with a 1- to 4-week recall period. Responses to 35 of the 36 items are used to compute an 8-domain scores and two component summary measures. The remaining item (the 'health transition' item), asks participants to rate how their current state of health compares to their state of health one year ago. This item is not used to calculate domain scores.

The 8-domains are: Physical Functioning (PF), Role Limitations due to Physical Health (RP), Bodily Pain (BP), General Health Perceptions (GH), Vitality (VT), Social Functioning (SF), Role Limitations due to Emotional Problems (RE), and Mental Health (MH). The component summary measures (physical component summary [PCS] and mental health component summary [MCS]) are computed from domain scores to give a broader metric of physical and mental health-related quality of life. The transformed score range for each of the 8 domains and for PCS and MCS is 0-100; higher scores indicate better health state.

The change from baseline in SF-36v2 (PCS and MCS) scores will be calculated.

The threshold values for the SF-36v2 PCS, MCS, and domain scores listed in [Table 3](#) are suitable for interpreting change at the participant level and are referred to as the responder thresholds or responder definitions (Maruish 2011).

**Table 3 Threshold values for the SF-36v2 scale and summary measures**

Threshold	SF-36v2 score									
	PCS	MCS	PF	RP	BP	GH	VT	SF	RE	MH
Group difference	2	3	3	3	3	2	2	3	4	3
Individual change	3.4	4.6	4.3	3.4	6.2	7.2	6.2	6.9	4.5	6.2

BP, bodily pain; GH, general health perceptions; MCS, mental health summary; MH, mental health; PCS, physical component summary; PF, physical functioning; RE, emotional problems; RP, role limitations due to physical health; SF, social functioning; VT vitality.

Categorical analyses of the change in each of the SF-36v2 scales and summary measures will be compared to its respective individual change threshold (see [Table 3](#)) to indicate whether each participant experienced a change deemed clinically significant and important. A participant will be classified as a responder if the change from baseline  $\geq$  individual change threshold, or a non-responder if change from baseline  $<$  individual change threshold. If data are missing, then the participant will be classified as a non-responder.

#### **3.5.1.4 Work Productivity and Activity Impairment questionnaire for OA (WPAI:OA)**

The WPAI:OA is a self-administered tool comprised of 6 questions that measure absenteeism, presenteeism, work productivity, and activity impairment due to OA of knee. This tool captures data from the past 7 days. Each subscale score is expressed as a percentage impairment from 0 to 100, where higher numbers indicate greater impairment and less productivity.

The following WPAI:OA impairment scores are defined: i) Percent activity impairment due to Osteoarthritis, ii) Percent impairment while working due to osteoarthritis, iii) Percent overall work impairment due to osteoarthritis and iv) Percent work time missed due to Osteoarthritis. Further details about the questions and derivations of those endpoints are shown in [Appendix A1](#).

#### **3.5.1.5 Healthcare Resource Utilisation (HCRU)**

Healthcare resource utilisation information (e.g., doctor office visits, hospitalisations, surgeries, or other procedures) used by each participant are collected by the investigator and study-site personnel for all participants at baseline (i.e., collecting data up to 3 months before) and various time points during the study as specified (See CSP Table 1). Protocol-mandated procedures, tests, and encounters are excluded. The responses and scores to the HRCU questionnaire are presented in [Appendix A2](#) with questions recalling the period between visits reported in weeks for all visits except for baseline.

#### **3.5.1.6 Lack of efficacy endpoints**

The investigator is responsible to determine if a participant should discontinue treatment due to lack of efficacy and report the same on the DS\_EOT page of eCRF.

For each participant, the time to permanent discontinuation of IP due to lack of efficacy will be determined as follows:

(Date of IP discontinuation as reported on the DS\_EOT page of eCRF) – (date of first IP administration) +1

### 3.5.1.7 Rescue medication use

Rescue medication (paracetamol) use will be collected via the participant eDiary from Day -14 until Week 18. Participants who discontinue IP early, will stop recording rescue medication after the ET visit.

The following variables will be derived and/or summarised:

- Number of participants using the rescue medication
- Reason for using rescue medication
- Total number of days rescue medication was used
  - Each day on which rescue medication was used at least once is counted
- Cumulative consumption (mg) of rescue medication use
  - Calculated as the total dose of rescue medication (mg)
- Average daily dose (mg) of rescue medication use
  - Calculated as: cumulative consumption of rescue medication (mg) /total number of days rescue medication was used

In addition to the above and in order to evaluate the changes in rescue medication use (number of days and cumulative consumption) over time, the daily collected data will be assigned to a specific study week. This assignment will use the same principles as deriving the NRS pain scores. For details refer to the section [3.2](#).

### 3.5.2 Biomarker and Pharmacodynamic variables

The biomarker endpoints are defined in the section [1.1.4](#).

However, only the below will be considered for analyses and CSR reporting depending on data availability at the end of the study (final clinical database lock):

- Total NGF measurements in serum over time (also denominated as pharmacodynamic variable/endpoint)
- Baseline biomarkers/pharmacodynamics namely Total NGF, TNF alpha, IL-1 beta, IL-6 and high sensitivity C-reactive protein (CRP)

Additional endpoints may be analysed providing such data are available.

Samples for biomarker research are required and will be collected from all participants in this study as specified (see CSP Table 1). Note that participants who discontinue IP early will have their last pharmacodynamics/biomarkers sampling at the ET visit.

### 3.5.3 Ambulatory blood pressure monitoring (ABPM) variables

The ABPM endpoints are presented in section 1.1.4.

During ABPM, the systolic BP, diastolic BP, pulse pressure, pulse rate recorded as heart rate by the vendor, and mean arterial pressure readings will be recorded over a period of 24 hours with frequency of readings during the day (every 15 minutes) and overnight (every 30 minutes). Participants will wear the ABPM device for a period of 24 hours at 2 separate times during the study: one time during the screening period and one time during the double-blind treatment period (between Weeks 8 and 12 inclusive).

An average of the individual readings during the day as well as the night will be determined for each participant. The 24-hour assessments will be derived as an overall average of all readings of a specific parameter for each participant for that specific visit (screening or visit within Weeks 8 and 12).

Individual readings with missing or zero values or values out of the acceptable ranges as identified in Table 4 below as well as those set to ‘not done’ will not be included in the calculation of averages.

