**Table 4 Acceptable ABPM ranges**

Parameter	ABPM acceptable ranges
Systolic blood pressure (SBP)	10 - 250 mmHg
Diastolic blood pressure (DBP)	5 - 200 mmHg
Pulse Pressure (PP)	5- 250 mmHg
Mean Arterial Pressure (MAP)	10 – 250 mmHg
Heart Rate (HR)	1 - 200 bpm

In addition, the entire set of the readings for a specific visit will be considered of poor quality and hence not used for analysis if any of the following is met:

- There is less than 20h of the total readings available for a specific parameter and visit for each participant

- There are less than 70% of valid measurements out of the total measurements recorded for a specific parameter and visit for each participant

Such readings that should be excluded will be identified by the vendor according to the above-mentioned criteria.

ABPM will be classified as normal if average is within normal reference range presented in [Table 5](#) below and abnormal if the average is outside of this reference range.

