**Table 6 Vital signs reference ranges**

Parameter	Standard Unit	Lower Limit	Upper Limit
Diastolic Blood Pressure	mmHg	60	120
Systolic Blood Pressure	mmHg	100	160
Pulse Rate	Beats/min	40	120
Respiratory Rate	Breaths/Min	8	28
Body Temperature	Celsius	36.5	38

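### Table 5 cannot flag a high heart-rate average, and practically cannot flag a high systolic one; separately, the unweighted 24-hour ABPM mean over-weights daytime

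*SAP*

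**What the plan says.** **Sampling and averaging (SAP section 3.5.3).** The device records over 24 hours "with frequency of readings during the day (every 15 minutes) and overnight (every 30 minutes". Two kinds of summary are formed. For day and night: "An average of the individual readings during the day as well as the night will be determined for each participant". For the whole day: "The 24-hour assessments will be derived as an overall average of all readings of a specific parameter". The SAP gives no time weighting.

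**Reading validity (section 3.5.3, Table 4).** Readings that are missing, zero, marked not done or outside Table 4 "will not be included in the calculation of averages". A whole recording is dropped if it covers less than 20 hours or has less than 70% valid measurements.

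**Classification (text after Table 4, and Table 5).** The average, not the single reading, is judged: "ABPM will be classified as normal if average is within normal reference range". For systolic pressure (SBP), diastolic pressure (DBP) and heart rate (HR), Table 5 uses the same limits for day, night and 24 hours.

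**Use (section 4.2.3.1).** SBP, DBP and pulse rate are analysed separately for day, night and 24 hours, with descriptive statistics and an ANCOVA of change from baseline. Participants' means and changes are listed, and abnormal values are flagged in that listing.

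**Comparison range (section 3.6.5, Table 6).** Clinic vital signs have their own, much narrower limits.

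**The concern.** A normal range for an average should be able to separate unusual participants from the rest. Table 5 is applied after Table 4 has removed extreme readings, and its upper limits sit at or close to those cut-offs. It is also far wider than the range the same SAP uses for a single clinic reading, although an average varies less than a single reading. A reader of the listing could take the absence of high flags as reassurance when the rule could hardly have produced one.

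The second issue is the meaning of the 24-hour value. Readings are twice as dense by day, so a plain mean gives each daytime hour twice the weight of each night hour. The result is presented and tested as a 24-hour quantity but leans towards daytime. If treatment acts differently by day and night, the 24-hour ANCOVA estimates a different mixture from the one its label suggests.

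**Working it through.** The SAP states no numerical result for ABPM that could be reproduced, so the check has two parts.

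**A. Can Table 5 flag a high average?**

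| Parameter | Table 4: reading kept | Table 5: average normal | Table 6: clinic reading |
|---|---|---|---|
| SBP, mmHg | 10–250 | 70–240 | 100–160 |
| DBP, mmHg | 5–200 | 40–150 | 60–120 |
| HR or pulse, per min | 1–200 | 20–200 | 40–120 |

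- *HR.* Every retained reading is at most 200, so the mean is at most 200. Table 5 calls 200 normal. A high flag is impossible.
- *SBP.* Let p be the share of retained readings at or below 200. The largest possible mean is 250(1 − p) + 200p = 250 − 50p. For this to exceed 240, p must be below 0.20. So more than 80% of the readings would have to lie between 200 and 250.
- *DBP.* The Table 4 cut-off of 200 leaves room above 150, so a high flag is arithmetically possible. It needs an average 30 mmHg above the upper limit for a single clinic reading (150 − 120).

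Illustration of scale, with n = 350 (section 1.3) and normal distributions whose means and SDs are assumptions, not taken from the SAP. The expected number outside limits L to U is 350 × [Φ((L − μ)/σ) + 1 − Φ((U − μ)/σ)].

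| Average | Assumed mean; SD | Outside Table 5 | Outside Table 6 limits |
|---|---|---|---|
| 24-h SBP | 130; 12–18 | 0.00–0.15 | 4.3–33.5 |
| 24-h DBP | 77; 8–12 | 0.00–0.36 | 5.9–27.5 |
| 24-h HR | 72; 9–13 | 0.00–0.01 | 0.1–2.5 |
| Night DBP | 68; 8–12 | 0.1–3.4 (all low) | 55.5–88.4 (all low) |

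The night DBP row shows that a low average, below 40, can still be flagged.

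**B. How far does the 24-hour mean lean towards daytime?**

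Inputs from section 3.5.3: 4 readings per hour by day and 2 per hour by night. Assumptions: D day hours between 14 and 18, and a day-night SBP difference of 10 to 20 mmHg.

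- Readings: 4D by day and 2(24 − D) by night.
- Night weight in the plain mean: 2(24 − D) / [4D + 2(24 − D)]. Night weight by time: (24 − D)/24.
- Level error = (night weight by time − night weight in plain mean) × day-night difference.

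| Day/night hours | Readings, day/night | Night weight, plain | Night weight, by time | Level error for 10; 20 mmHg | Night-only change lost | Day-only change inflated |
|---|---|---|---|---|---|---|
| 14/10 | 56/20 | 26.3% | 41.7% | 1.5; 3.1 mmHg | 37% | 26% |
| 16/8 | 64/16 | 20.0% | 33.3% | 1.3; 2.7 mmHg | 40% | 20% |
| 18/6 | 72/12 | 14.3% | 25.0% | 1.1; 2.1 mmHg | 43% | 14% |

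The last two columns are 1 minus the ratio of the night weights, and the ratio of the day weights minus 1. At 16/8 these are 1 − 20.0/33.3 and 80.0/66.7 − 1.

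*Change from baseline at 16/8.* The error is 0.133 × the change in the day-night difference. A 5 mmHg fall at night only appears as 5 × 0.20 = 1.0 instead of 5 × 0.333 = 1.67. A 5 mmHg fall by day only appears as 4.0 instead of 3.33. A 5 mmHg fall in both appears as 5.0, without error.

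*Different valid readings at the two visits.* The 20-hour and 70% rules appear to allow four night hours to be lost: 20 hours remain, and 72 of 80 readings is 90%. With assumed means of 130 by day and 115 by night at both visits, the complete recording gives (64 × 130 + 16 × 115)/80 = 127.0. The incomplete one gives (64 × 130 + 8 × 115)/72 = 128.3. That is a change of 1.3 mmHg where none occurred. Day and night means weighted by hours give (16 × 130 + 8 × 115)/24 = 125 at both visits.

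**The case against.** The averaging rule is explicit, computable and contradicted nowhere in the SAP. A reader might infer that the 24-hour output is simply wrong; the document does not support that. The value is what section 3.5.3 defines it to be, and the criticism is that it describes the 24-hour mean poorly. The level shift largely cancels in change from baseline, because both visits use the same schedule. Day and night means have their own ANCOVAs in section 4.2.3.1, so a night-only effect appears in full there. The validity rules also limit how far reading patterns can differ. All of this stands. What remains is the case where day and night respond differently, and the case where valid night readings differ between visits. The latter adds noise, or bias if the loss differs by arm.

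On Table 5, a reader might infer that no abnormal value can ever be flagged. That goes too far: a night DBP average below 40 can be. A reader might also infer that Tables 5 and 6 contradict each other. They cover different measurements, so this is an unexplained contrast, not a contradiction. That Table 5 looks like a plausibility range is an inference. The listing prints the means themselves, so an extreme value stays visible whether or not it is flagged. None of this rescues the HR upper limit, which fails by arithmetic within the SAP's own tables.

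**Conclusion.** Both points hold in limited form and are minor, because ABPM is exploratory and neither touches the primary or key secondary endpoints.

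Table 5 is wrong as written for high averages. This is certain for HR and practically so for SBP, and it needs no outside assumption beyond the SAP's own limits. The consequence is confined to a flag in a listing.

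The unweighted 24-hour mean is a weak derivation that costs nothing to improve. The doubled daytime weight per hour follows directly from the schedule. The sizes (night weight 20% against 33%, level error of roughly 1 to 3 mmHg, 40% dilution or 20% inflation of a one-sided change) rest on assumed window lengths and an assumed day-night difference. They vary over the ranges shown. The separate day and night analyses are unaffected by the weighting.

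**What to change.** 1. Reconcile Table 5 with Tables 4 and 6, so that the range applied to averages can identify abnormal values on both sides. Check all five Table 5 parameters, including pulse pressure and mean arterial pressure. Keep reading-validity limits in Table 4. If Table 5 is meant as a plausibility check, label it so. The limits themselves are for clinical agreement.
2. In section 3.5.3, define the 24-hour value as a time-weighted mean: either the mean of hourly means, or the day and night means weighted by the hours in each window. Apply it to every ABPM parameter at both visits.

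Cost: one table, a sentence in section 3.5.3, and a change to derivation code or the vendor specification. No new data are needed.

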**Table 4 Acceptable ABPM ranges**

Parameter	ABPM acceptable ranges
Systolic blood pressure (SBP)	10 - 250 mmHg
Diastolic blood pressure (DBP)	5 - 200 mmHg
Pulse Pressure (PP)	5- 250 mmHg
Mean Arterial Pressure (MAP)	10 – 250 mmHg
Heart Rate (HR)	1 - 200 bpm

In addition, the entire set of the readings for a specific visit will be considered of poor quality and hence not used for analysis if any of the following is met:

- There is less than 20h of the total readings available for a specific parameter and visit for each participant

- There are less than 70% of valid measurements out of the total measurements recorded for a specific parameter and visit for each participant

Such readings that should be excluded will be identified by the vendor according to the above-mentioned criteria.

ABPM will be classified as normal if average is within normal reference range presented in [Table 5](#) below and abnormal if the average is outside of this reference range.

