#### **4.2.3.1 ABPM**

Three ABPM parameters (systolic and diastolic blood pressure and pulse rate) will be evaluated separately for during daytime, night-time and over the 24-hour period as follows:

- Baseline and change from baseline will be summarised descriptively as per section 4.1
- ANCOVA for change from baseline with treatment and baseline ABPM as covariates will be fitted and results including 95% CIs and nominal p-values tabulated.

Absolute mean ABPM values and ABPM mean change from baseline for readings mentioned in section 3.5.3 will be listed for each participant. Abnormal values as defined in section 3.5.3 will be flagged within the listing.

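### ABPM quality is judged on the pooled 24-hour recording although day, night and 24-hour averages are analysed separately, so a poor night can pass and a complete night can be discarded

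*SAP*

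**What the plan says.** Section 3.5.3 sets readings every 15 minutes by day and every 30 minutes overnight. "Participants will wear the ABPM device for a period of 24 hours at 2 separate times during the study", once in screening and once between Weeks 8 and 12.

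Three averages are derived per parameter. For the two periods, "An average of the individual readings during the day as well as the night will be determined for each participant". For the whole recording, "The 24-hour assessments will be derived as an overall average of all readings of a specific parameter for each participant".

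Missing, zero, out-of-range and not-done readings are left out of the averages. After Table 4, two further rules decide whether a recording is used at all. If either is met, "the entire set of the readings for a specific visit will be considered of poor quality and hence not used for analysis". The first rule concerns duration and applies when "There is less than 20h of the total readings available for a specific parameter and visit for each participant". The second concerns validity, is likewise set on the pooled recording, and applies when "There are less than 70% of valid measurements out of the total measurements recorded for a specific parameter and visit for each participant".

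The vendor identifies the exclusions. No rule is set for day or night alone, and no minimum number of night readings is given.

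Section 4.2.3.1 states that systolic pressure, diastolic pressure and pulse rate "will be evaluated separately for during daytime, night-time and over the 24-hour period as follows". Each average gets a descriptive summary and an ANCOVA of change from baseline.

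**The concern.** Quality is judged on one unit and the outcomes are analysed on another. One pooled verdict covers three averages, two of which use only part of the recording. The pool is mostly daytime readings, so good day data can carry a poor night through, and poor day data can remove a good night.

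Two things are at stake. A night mean may rest on half or fewer of its planned readings, and a 24-hour mean may be largely or wholly a daytime mean, while both enter the ANCOVA on the same footing as complete recordings. In the other direction, usable night averages are lost. Because the outcome is a change from baseline, losing either the screening or the on-treatment recording removes that participant from the night-time comparison.

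**Working it through.** **Inputs from section 3.5.3.** 4 readings per hour by day, 2 per hour at night, 24 h worn; exclusion below 20 h or below 70% valid.

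**Assumptions.** The SAP does not state the day and night windows. I take 16 h/8 h and show a range. For the mmHg figures I assume a day systolic mean of 135 mmHg, a night dip of 10-20 mmHg, and a within-night SD of 8-12 mmHg with independent readings.

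The plan gives thresholds here but no derived figure to reproduce.

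**Step 1: reading counts.** With D day hours, day readings = 4D, night readings = 2(24 − D), total = 2D + 48. At D = 16: 64 + 16 = 80.

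**Step 2: the 70% rule with no valid night reading.** Valid share = 4D/(2D + 48) = 2D/(D + 24). At D = 16: 64/80 = 80.0%, a pass. Break-even: 2D = 0.7(D + 24), so D = 16.8/1.3 = 12.92 h, a night of 11.08 h. Any shorter night can be wholly invalid and still satisfy this rule.

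**Step 3: add the 20 h rule.** A recording must satisfy both rules.
- If the rule counts recorded hours, a full 24 h recording with a wholly invalid night has 24 h and 80% valid. It passes both.
- If it counts valid hours, only 16 h remain and the set is excluded. But 4 h may still be lost, all at night: 16 h + 4 h = 20 h, with (64 + 8)/80 = 90% valid. A night with 8 of 16 valid readings (50%) passes both.

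**Step 4: the reverse case.** With a complete night, the set is dropped when daytime validity is below (0.7 × total − night)/day. At 16 h/8 h: (56 − 16)/64 = 62.5%, that is, fewer than 40 of 64. Check: (39 + 16)/80 = 68.75% fails; (40 + 16)/80 = 70% passes. This follows from the 70% rule alone, so it holds under either reading of the 20 h rule.

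| Day/night (h) | Readings day + night | Valid share, no valid night reading | Night share that still passes if 20 h means valid hours and the day is perfect | Daytime validity below which a complete night is dropped |
|---|---|---|---|---|
| 18/6 | 72 + 12 | 85.7% | 33% | 65.0% |
| 16/8 | 64 + 16 | 80.0% | 50% | 62.5% |
| 14/10 | 56 + 20 | 73.7% | 60% | 59.3% |
| 13/11 | 52 + 22 | 70.3% | 64% | 57.3% |
| 12/12 | 48 + 24 | 66.7% (fails) | 67% | 55.0% |

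The fourth column is (20 − D)/(24 − D).

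**Step 5: size in an affected participant (16 h/8 h).** The 24-hour value is an unweighted mean of readings.
- Complete recording: 135 − dip × 16/80 = 133 (dip 10) or 131 (dip 20).
- No valid night reading: 135, so 2-4 mmHg too high.
- 8 valid night readings: 135 − dip × 8/72 = 133.9 or 132.8, so 0.9-1.8 mmHg too high.
- Standard error of the night mean, SD/√m: 2-3 mmHg from 16 readings, 2.8-4.2 mmHg from 8.

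**The case against.** The strongest objection is that the two rules act together. Section 3.5.3 already strips unusable readings from the averages, so it is natural to take the 20 h rule as usable hours. A lost 8 h night then leaves 16 h and the set is rejected. This stands as one of two open readings. The 20 h rule speaks of readings available and the next rule of valid measurements, and the SAP does not say whether these mean the same. On the milder reading the gap narrows to nights about half complete, but it does not close.

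A reader might infer that night averages with no valid readings enter the ANCOVA. They cannot: with no valid night reading there is no night mean, and only the 24-hour mean is affected.

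A reader might also infer that the dose-placebo comparison is biased whenever screening and Week 8-12 recordings lose different periods. The documents do not support that. Such loss shifts an individual's change score, but the trial is randomised and double-blind and the ANCOVA adjusts for baseline ABPM. Bias between arms needs loss that differs by arm, and nothing in the SAP suggests it.

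Three further points stand. Nothing shows how often validity fails in one period only. Rejecting a recording with many bad daytime readings is a defensible conservative choice, although it costs a sound night average. The ABPM endpoint section is redacted and the vendor specification is not shown, so either may define periods and hours more closely.

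**Conclusion.** The mismatch is real but minor. Both quality rules act on the pooled recording, while three averages are analysed separately. The pooled 70% rule does not protect the night for any night shorter than about 11.1 h. What gets through depends on the undefined 20 h rule: a wholly invalid night if it counts recorded hours, or a half-valid 8 h night if it counts valid hours. The discarding of complete nights does not depend on that reading.

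The consequence is added noise and lost data. The pass/fail counts rest on the SAP's reading frequencies and the assumed windows; the mmHg figures also rest on the assumed day level, dip and SD. How many participants would be affected is unknown. ABPM is exploratory with nominal p-values, so none of the tested hypotheses H1 to H10 is touched.

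**What to change.** 1. State whether the 20 h rule counts recorded hours or hours with valid readings.
2. Apply the validity threshold, or a minimum number of valid readings, separately to day and to night. State whether the denominator is scheduled or recorded readings; the present rule uses recorded ones, so readings never taken do not count against the 70%.
3. Require both periods to pass before the 24-hour average is used.
4. Let a failed period remove only its own average and the 24-hour average.
5. Give the vendor the same wording and re-run the exclusion flags.

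The cost is a short SAP and vendor-specification change and one re-run of flags. Some night and 24-hour averages will become missing, partly offset by day or night averages that the pooled rule now discards.
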